## 5.4 Visual Acuity and External Eye Exam

Frequency and percent of visual acuity abnormality will be presented by treatment for the pre-dose (screening) and post-dose assessments in [Table 5.1.1](#) for the study eye.

Frequency and percent of visual acuity abnormality will be presented by treatment for the pre-dose (screening) and post-dose assessments in [Table 5.1.2](#) for the fellow eye.

Frequency and percent of eye exam abnormality will be presented by treatment for each category of iris, pupil, and lens at the pre-dose (screening) and post-dose assessments in [Table 5.2.1](#) for the study eye.

Frequency and percent of eye exam abnormality will be presented by treatment for each category of iris, pupil, and lens at the pre-dose (screening) and post-dose assessments in [Table 5.2.1](#) for the fellow eye.

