### 1.2 *Potential Risks and benefits to human subjects*

Minimal risks are expected with AG-920. Based upon clinical trials conducted to date, expected risks for subjects may include temporary, mild conjunctival/ocular hyperemia, eye pain, instillation site reaction (stinging/burning), and conjunctival hemorrhage upon instillation of the investigational medicinal product (IMP). For any additional information on AG-920 use, please refer to the [Investigator's Brochure](#).

Minimal risks are expected with the comparator, Proparacaine HCl ophthalmic solution. Occasional temporary stinging, burning and conjunctival redness may occur with the use of Proparacaine. A rare, severe, immediate-type, apparently hyperallergic corneal reaction (characterized by acute, intense and diffuse epithelial keratitis, a gray, ground glass appearance, sloughing of large areas of necrotic epithelium, corneal filaments and, sometimes, iritis with descemetitis) has been reported. Allergic contact dermatitis from Proparacaine with drying and fissuring of the fingertips has also been reported. For any additional information on Proparacaine use, please refer to the [Package Insert](#).

As this study is to be conducted in healthy pediatric subjects, there is no anticipated benefit other than the possibility that a subject's participation in the present study may help others in the future to have more options for local anesthesia before ophthalmic procedures.

Any new, unexpected adverse events (AEs) present among subjects in this clinical trial will be communicated to Investigators and to ethics committees or Institutional Review Board (IRBs) in accordance with local regulations.

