#### 6.4.3.2 15-60 minutes Post Treatment

Fifteen (15) to 60 minutes after the eye exam, the following examinations will be performed

- Visual Acuity
- External eye exam
- Slit lamp biomicroscopy ONLY if necessary for a suspected AE
- Assess for adverse events and changes in medications
- Schedule Follow-up Phone Call between Days 2-5 (1-4 days following dosing).

*Windows: Times will be measured to the nearest minute*

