### 9.4.7 Analysis of Safety

External eye exam measures and slit lamp biomicroscopy (if applicable) will be summarized at each measured time point using discrete summary statistics.

Visual Acuity data will be summarized at each time point organized by the age and clinically appropriate test, which may be continuous, categorical or both.

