**Procedures: External Eye Exam and Biomicroscopy**

[REDACTED]

[REDACTED]

[REDACTED]

[REDACTED]

[REDACTED]

Grading will be done as follows:

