#### Bio-microscopy (Slit-Lamp)

Where available, total severity scores of bio-microscopy (Slit-Lamp of seven items on grading scale, including lid erythema, lid edema, conjunctiva hyperemia, conjunctiva edema, corneal edema, anterior chamber cells, and anterior chamber flare) will be summarized by treatment for Day 1 (post-dose), using a number of observations, mean, standard deviation, minimum, median, and maximum values. The analysis will be based on the safety population defined in [Section 3.1](#). Note that biomicroscopy is only performed if an Adverse Event is suspected by the Investigator. For those subjects with no bio-microscopy test performed on Day 1, the total severity scores will be set to zero for the purpose of the analysis.

For both study eye and fellow eye, the total severity score at post-dose will be analyzed for differences between AG-920 and active-control groups, using analysis of variance (ANOVA).

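### SAP 5.4 limits the by-treatment external eye exam tables to iris, pupil and lens, leaving no exam summary by arm of the conjunctival signs the protocol expects

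*SAP*

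**What the plan says.** **Which examinations are done.** Protocol Table 1 schedules the external eye exam at screening and again after dosing. Protocol 6.1 has ocular assessments done on both eyes. For the post-dose step, Protocol 6.4.3.2 states: "Fifteen (15) to 60 minutes after the eye exam, the following examinations will be performed". The list contains visual acuity, the external eye exam and "Slit lamp biomicroscopy ONLY if necessary for a suspected AE". Table 1 schedules no slit lamp before dosing.

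**What is expected.** For AG-920, Protocol 1.2 names "temporary, mild conjunctival/ocular hyperemia, eye pain, instillation site reaction (stinging/burning), and conjunctival hemorrhage upon instillation". For the comparator: "Occasional temporary stinging, burning and conjunctival redness may occur with the use of Proparacaine".

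**How the exam is to be summarized.** Protocol 9.4.7: "External eye exam measures and slit lamp biomicroscopy (if applicable) will be summarized at each measured time point using discrete summary statistics". SAP 2.9.3 refers to external eye exam abnormality in general, by treatment, at screening and post-dose. SAP 5.4 is more specific. It presents abnormality by treatment "for each category of iris, pupil, and lens at the pre-dose (screening) and post-dose assessments", once for the study eye and once for the fellow eye, and cites Table 5.2.1 both times.

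**Where lid, conjunctiva and cornea appear.** Protocol Appendix 1 prints grading scales for lid, conjunctiva, cornea and anterior chamber under the heading "Procedures: External Eye Exam and Biomicroscopy". The procedure text between that heading and the scales is blacked out. The SAP uses these seven graded items only in the slit-lamp total score, with the caution: "Note that biomicroscopy is only performed if an Adverse Event is suspected by the Investigator". Children without a slit-lamp test score zero (SAP 2.9.3 and 5.5).

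**The concern.** The three structures with rows in the exam tables are not the ones on which the protocol expects visible local effects. A programmer building the tables from SAP 5.4 would make rows for iris, pupil and lens and none for conjunctiva. A red conjunctiva found on the required post-dose exam, with no slit lamp done, would then have no row in the exam tables and would count as zero in the slit-lamp table.

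At stake is a systematic comparison of local signs between arms, with a pre-dose reference, in both eyes. Safety and tolerability is the secondary objective, and Protocol 8.1 lists the external eye exam among the safety parameters.

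**Working it through.** The plan gives no figure here and no arithmetic is needed beyond counting. The check sets the passages side by side.

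**Step 1: overlap between table rows and graded signs.** SAP 5.4 names 3 structures: iris, pupil, lens. SAP 2.9.3 lists 7 slit-lamp items, matching the Appendix 1 scales: lid erythema, lid edema, conjunctival hyperemia, conjunctival edema, corneal edema, anterior chamber cells, anterior chamber flare. Items concerning iris, pupil or lens: 0 of 7.

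**Step 2: overlap between table rows and expected effects.** Protocol 1.2 names four effects for AG-920. Two are visible conjunctival signs (hyperemia, hemorrhage); the others are eye pain and instillation site reaction. For Proparacaine, the common effects are stinging, burning and conjunctival redness. None of the conjunctival signs falls under iris, pupil or lens.

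**Step 3: SAP against protocol.** Protocol 9.4.7 covers the exam's measures without naming structures. SAP 5.4 is therefore narrower if the exam records anything beyond the three. SAP 2.9.3 and the titles of Tables 5.2.1 and 5.2.2 are general, and the shells are not supplied, so SAP 5.4 is the only text that names rows.

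**Step 4: does another output give the missing summary?**

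| Output | Every child? | By arm? | Pre- and post-dose? | Shows conjunctival signs? |
|---|---|---|---|---|
| Tables 5.2.1 and 5.2.2 as SAP 5.4 describes them | Yes | Yes | Yes | No row |
| Slit-lamp score, Tables 6.1.1 and 6.1.2 | Tested only for a suspected AE; otherwise zero | Yes | Post-dose only | Only within a total |
| TEAE tables 4.2.5 and 4.2.6 | If reported as an AE | Yes | Post-dose onset only | Yes, if reported |
| Listing 16.2.6.3 | Yes | By subject, no summary | As collected | As collected |

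No row of the table has all four properties.

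**Step 5: does the external exam look beyond iris, pupil and lens?** The documents do not settle this, because the procedure text is blacked out. Indirect evidence suggests that it does. Eligibility requires a normal cornea and excludes current ocular inflammation (Protocol 4.1 and 4.2), screening includes no slit lamp, and the external exam is the only listed screening examination of eye structures (Protocol 6.3). This is an inference.

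**The case against.** The strongest reply is that the adverse event route already covers these signs. Protocol 8.3.1 counts abnormal examination findings as events to be documented, and adverse events are assessed in the same 15-60 minute step as the external exam. New redness seen there should be recorded, would fall on the dosing day and so inside the SAP's treatment-emergent window, and would be tabulated by arm and by eye. The secondary endpoints are themselves incidences of adverse events, so exam tables are supportive. The investigator is not masked in this trial, and extra exam rows would not change that. All of this stands, and it keeps the point small. It does not supply the exam summary: adverse event tables depend on a decision to report and give no pre-dose findings for comparison.

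Four stronger readings are tempting, and the documents do not support them.

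- A reader might infer that these signs are never reported. They are: the exam data go into Listing 16.2.6.3, Protocol 9.7 lists all database data, and signs reported as adverse events reach the TEAE tables.
- A reader might infer that lid signs are also expected from the drop. Protocol 1.2 names no lid sign for either product. Lid items appear only in the Appendix 1 scales and the slit-lamp score.
- A reader might infer that the tolerability comparison will be understated. That is not shown. It runs mainly through the TEAE tables, and the documents give no rate of visible redness from which to size any loss. Hyperemia is described as temporary, so some may have cleared by the time of the exam.
- A reader might infer that Appendix 1 proves the external exam grades lid, conjunctiva and cornea. The shared heading does not say which exam uses which scale. The SAP attaches the scales to the slit lamp, and the blacked-out text is not a fault in the plan.

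**Conclusion.** The point holds as a modest reporting gap. Followed as written, SAP 5.4 gives no summary by arm, pre- versus post-dose, of the conjunctival signs that Protocol 1.2 expects, from the only eye-structure exam scheduled for every child at both times. It is narrower than Protocol 9.4.7, and the slit-lamp score does not fill the gap.

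The size is three tabulated structures, none of them the site of an expected conjunctival sign. The finding depends on no assumed event rate and affects neither the primary analysis nor the adverse event endpoints.

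It rests on two assumptions: that SAP 5.4 governs the rows, since the shells are not available, and that the external exam records the conjunctiva, which is likely but unconfirmed. If the CRF collects only iris, pupil and lens, the SAP table matches the data, and the mismatch lies between what the exam captures and what Protocol 1.2 expects. The sponsor would then need to address that explicitly.

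**What to change.** Reconcile SAP 5.4 with Protocol 9.4.7, Appendix 1 and the CRF. In Tables 5.2.1 (study eye) and 5.2.2 (fellow eye), tabulate every structure the external exam records, by arm and time point. Include conjunctiva, cornea and lid where they are collected, and keep iris, pupil and lens. Use the Appendix 1 grades only if that exam is graded; otherwise show normal or abnormal.

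In the same edit, change the fellow-eye citation in SAP 5.4 from Table 5.2.1 to Table 5.2.2, as in the SAP's own list of tables.

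The cost is SAP wording, a few more table rows and a CRF check. Tabulating what is already recorded needs no new procedure or visit.

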### **5.5 Bio-microscopy**

For those subjects with no bio-microscopy test performed on Day 1, the total severity scores will be set to zero for the purpose of the analysis.

Descriptive and inferential statistics of bio-microscopy (Slit-Lamp) total severity score will be presented by treatment for the post-dose assessments in [Table 6.1.1](#) for the study eye.

Descriptive and inferential statistics of bio-microscopy (Slit-Lamp) total severity score will be presented by treatment for the post-dose assessments in [Table 6.1.2](#) for the fellow eye.

### **5.6 Concomitant Medication**

Number and percent of subjects who take pre-randomization concomitant medications will be reported in [Table 7.1.1](#). Number and percent of subjects who take post-randomization concomitant medications will be reported by treatment in [Table 7.1.2](#). Number and percent of subjects who take post-treatment concomitant medications will be reported by treatment in [Table 7.1.3](#).

Number and percent of subjects who take post-randomization concomitant medications for eye treatment will be reported in [Table 7.2.1](#) for study eye and in [Table 7.2.2](#) for fellow eye.

## 7 List of Statistical Table Shells

Statistical table shells are provided after the text portion. Table shells are presented only for those tables with a unique format. Tables with duplicate formats are indicated in the list of tables below. Final TFL sets will be numbered with the ICH E3 title as listed below.

Table Title (SAP)	ICH E3 Title for Section 14 (TFL)
Table 1.1.1 Screen Summary	Table 14.1.1.1
Table 1.1.2 Enrollment Summary: Enrolled/Randomized population	Table 14.1.1.2
Table 1.1.3 Randomized Treatment Summary: Safety population	Table 14.1.1.3
Table 1.1.4 Randomized Complete Treatment Summary: ITT population	Table 14.1.1.4
Table 1.1.5 Randomized As-Treated Summary: PP population	Table 14.1.1.5
Table 1.2.1 Demography: Enrolled/Randomized population	Table 14.1.2.1.1
Table 1.2.2 Demography: Safety population	Table 14.1.2.1.2
Table 1.2.3 Demography: ITT population	Table 14.1.2.1.3
Table 1.2.4 Demography: PP population	Table 14.1.2.1.4
Table 1.3.1 Baseline Eye Characteristics: Safety population	Table 14.1.2.2.1
Table 1.3.2 Baseline Eye Characteristics: ITT population	Table 14.1.2.2.2
Table 1.3.3 Baseline Eye Characteristics: PP population	Table 14.1.2.2.3
Table 1.4.1 Disposition: Safety population	Table 14.1.3.1
Table 1.4.2 Disposition: ITT population	Table 14.1.3.2
Table 1.5.1 Protocol Deviations: ITT population	Table 14.1.6.1
Table 1.5.2 Treatment Compliance: Safety population	Table 14.1.6.2
Table 1.5.3 Treatment Compliance: ITT population	Table 14.1.6.3
Table 1.6.1 Summary of Missing Anesthetic Effect Status for the Study: ITT Population	Table 14.1.6.4
Table 2.1.1 Summary and Analysis of Proportion of Subjects with Anesthetic Effect at 2-4 Minutes Post Dose (LOCF): ITT population	Table 14.2.1.1
Table 2.1.2 Summary and Analysis of Proportion of Subjects with Anesthetic Effect at 2-4 Minutes Post Dose (Actual): PP population	Table 14.2.1.2
Table 2.1.3 By-Site Summary of Proportion of Subjects with Anesthetic Effect (LOCF)	Table 14.2.1.3
Table 2.2.1 Summary and Analysis of Proportion of Subjects with Anesthetic Effect at 2-4 Minutes Post Dose: Boys	Table 14.2.2.1
Table 2.2.2 Summary and Analysis of Proportion of Subjects with Anesthetic Effect at 2-4 Minutes Post Dose: Girls	Table 14.2.2.2
Table 2.2.3 Summary and Analysis of Proportion of Subjects with Anesthetic Effect at 2-4 Minutes Post Dose: Subjects aged 8-	Table 14.2.2.3
Table 2.2.4 Summary and Analysis of Proportion of Subjects with Anesthetic Effect at 2-4 Minutes Post Dose: Subjects aged 9+	Table 14.2.2.4
Table 2.2.5 Summary and Analysis of Proportion of Subjects with Anesthetic Effect at 2-4 Minutes Post Dose: Caucasian	Table 14.2.2.5
Table 2.2.6 Summary and Analysis of Proportion of Subjects with Anesthetic Effect at 2-4 Minutes Post Dose: Non-Caucasian	Table 14.2.2.6
Table 2.2.7 Summary and Analysis of Proportion of Subjects with Anesthetic Effect at 2-4 Minutes Post Dose: Iris Color Dark Brown	Table 14.2.2.7
Table 2.2.8 Summary and Analysis of Proportion of Subjects with Anesthetic Effect at 2-4 Minutes Post Dose: Iris Color Other	Table 14.2.2.8
Table 3.1.1 Treatment Exposure of All Applications: Safety population	Table 14.1.3.3
Table 4.1.1 Overall Summary of Adverse Events: Subjects Enrolled	Table 14.3.1.1

Table Title (SAP)	ICH E3 Title for Section 14 (TFL)
Table 4.1.2 Overall Summary of Adverse Events: Safety population	Table 14.3.1.2
Table 4.2.1 Incidence of Pre-Treatment AEs by Preferred Terminology	Table 14.3.1.3
Table 4.2.2 Incidence of Treatment-Emergent AEs by Preferred Terminology	Table 14.3.1.4
Table 4.2.3 Treatment-Emergent AEs with >5% Subjects Reporting by Preferred Terminology	Table 14.3.1.5
Table 4.2.4 Incidence of Subjects Reporting Post-Treatment AEs by Preferred Terminology	Table 14.3.1.6
Table 4.2.5 Incidence of Subjects Reporting Study-Eye Treatment-Emergent AEs by Preferred terminology	Table 14.3.1.7
Table 4.2.6 Incidence of Subjects Reporting Fellow-Eye Treatment-Emergent AEs by Preferred terminology	Table 14.3.1.8
Table 4.3.1 Incidence of Treatment-Emergent AEs and Onset Time	Table 14.3.1.9
Table 4.3.2 Incidence of Study-Eye Treatment-Emergent AEs and Onset Time	Table 14.3.1.10
Table 4.3.3 Incidence of Fellow-Eye Treatment-Emergent AEs and Onset Time	Table 14.3.1.11
Table 4.4.1 Treatment-Emergent AEs by Severity and Relationship to Study Treatment	Table 14.3.1.12
Table 4.4.2 Incidence of Treatment-Emergent AEs Associated with Discontinuations by Preferred Terminology	Table 14.3.2.3.1
Table 4.4.3 Incidence of Treatment-Emergent SAEs by Preferred Terminology	Table 14.3.2.2.1
Table 4.4.4 Incidence of Study-Eye Treatment-Emergent AEs Associated with Discontinuations and by Preferred Terminology	Table 14.3.2.3.2
Table 4.4.5 Incidence of Study-Eye Treatment-Emergent SAEs by Preferred Terminology	Table 14.3.2.2.2
Table 4.4.6 Incidence of Fellow-Eye Treatment-Emergent AEs Associated with Discontinuations and by Preferred Terminology	Table 14.3.2.3.3
Table 4.4.7 Incidence of Fellow-Eye Treatment-Emergent SAEs by Preferred Terminology	Table 14.3.2.2.3
Table 5.1.1 Summary of Visual Acuity Abnormalities: Study Eye	Table 14.3.4.1
Table 5.1.2 Summary of Visual Acuity Abnormalities: Fellow Eye	Table 14.3.4.2
Table 5.2.1 Summary of External Eye Exam Abnormalities: Study Eye	Table 14.3.5.1
Table 5.2.2 Summary of External Eye Exam Abnormalities: Fellow Eye	Table 14.3.5.2
Table 6.1.1 Summary and Analysis of Slit-Lamp Severity Scores: Study Eye	Table 14.3.6.1
Table 6.1.2 Summary and Analysis of Slit-Lamp Severity Scores: Fellow Eye	Table 14.3.6.2
Table 7.1.1 Summary of Pre-Randomization Concomitant Medication Use: Safety population	Table 14.1.5.1
Table 7.1.2 Summary of Post-Randomization Concomitant Medication Use: Safety population	Table 14.1.5.2
Table 7.1.3 Summary of Post-Treatment Concomitant Medication Use: Safety population	Table 14.1.5.3
Table 7.2.1 Summary of Pre-Randomization Study-Eye Concomitant Medication Use: Safety population	Table 14.1.5.4
Table 7.2.2 Summary of Pre-Randomization Fellow-Eye Concomitant Medication Use: Safety population	Table 14.1.5.5
Table 7.3.1 Summary of Post-Randomization Study-Eye Concomitant Medication Use: Safety population	Table 14.1.5.6
Table 7.3.2 Summary of Post-Randomization Fellow-Eye Concomitant Medication Use: Safety population	Table 14.1.5.7

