**Secondary Endpoints**

Incidence of AEs, TEAEs, SAEs, withdrawals due to TEAEs

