### 8.3 Adverse events

All AEs occurring after the first dose of IMP and throughout the remainder of the study period (Follow-up Phone Call) will be considered TEAEs and must be documented on the relevant Electronic Data Capture (EDC) pages and in the source documents. Whenever possible, the diagnosis, if available, and not the symptoms should be reported as the AE. AEs and Serious Adverse Events (SAEs) will be coded according to the Medical Dictionary for Regulatory Activities (MedDRA).

Documentation of adverse events/adverse reactions includes start date and stop date, severity, action(s) taken, seriousness and outcome.

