### 9.4.8 Adverse Events

Verbatim descriptions of AEs will be mapped to MedDRA thesaurus terms and presented in a data listing. Treatment emergent AEs, those that occur after the first dose of study medication, will be summarized by treatment group using frequency counts and percentages for each System Organ Class (SOC) and Preferred Term (PT) within each SOC. Summaries will be presented separately for ocular and non-ocular AEs. These summaries will also be presented by the relationship to the

Investigational Medicinal Product (related, unrelated) and by severity of the AE (mild, moderate, severe). Fisher's exact test will be used to test the difference in proportions of subjects with each AE between treatment groups (SOC and PT).

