#### Adverse Events

Adverse events will be coded for preferred terminologies using Medical Dictionary for Regulatory Activities (MedDRA). AEs will be grouped into pre-treatment AEs, treatment-emergent AEs, and post-treatment AEs and will be reported separately, based upon the start date and time of the events compared to the start date and time of the treatment.

Adverse events will be defined as pre-treatment AEs if they occur prior to the treatment start date and time; as treatment-emergent AEs if they occur on or after the treatment start date and time and before the next day; and as post-treatment AEs if they occur after the treatment date.

Frequency of treatment-emergent AEs will be calculated for each body system, by preferred terminology, by treatment group, for number of subjects and percentage reporting the event.

The severity of the adverse events and the relationship to the investigational product will be summarized for each body system and preferred terminology by treatment group. Withdrawals due to adverse events will be summarized for each body system and preferred terminology by treatment group and will be listed with demographic variables for individual subjects.

Serious adverse events (SAE) (including deaths) will be listed for individual events.

Narratives will be provided for all deaths, non-fatal serious adverse events, and subjects withdrawn due to adverse events.

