## 5.3 Adverse Events

An overall summary of AEs reported in this study will be provided in [Table 4.1.1](#) for study participants and in [Table 4.1.2](#) for the safety population. The incidences of subjects reporting pre-treatment AEs will be reported in [Table 4.2.1](#) for the pre-randomization period and in [Table 4.2.2](#) for the treatment-emergent AEs by treatment. Those treatment-emergent AEs by preferred terminology that are reported by more than 5% of subjects in any treatment will be tabulated in [Table 4.2.3](#).

Incidences of subjects reporting treatment-emergent AEs (TEAEs) will also be tabulated by treatment for the TEAEs associated with the study eye in [Table 4.2.5](#) and for the TEAEs associated with fellow eye in [Table 4.2.6](#).

Incidences of subjects reporting treatment-emergent AEs will also be tabulated by onset time (on-dosing day vs. post-dosing day) in [Table 4.3.1](#) for all TEAEs, and in [Table 4.3.2](#) for the TEAEs associated with the study eye, and in [Table 4.3.3](#) for the TEAEs associated with the fellow eye.

The severity of the treatment-emergent AEs and the relationship to the investigational product will be summarized in [Table 4.4.1](#).

Treatment-emergent AEs associated with early terminations and serious AEs will be summarized by preferred term, respectively, in [Table 4.4.2](#) and [Table 4.4.3](#) for all TEAEs, in [Table 4.4.4](#) and [Table 4.4.5](#) for the TEAEs associated with the study eye, and in [Table 4.4.6](#) and [Table 4.4.7](#) for the TEAEs associated with the fellow eye.

Details of AEs associated with both study and fellow eyes will be listed for each subject ([Listing 7](#))

Details of AEs associated with early terminations will be listed for each subject ([Listing 8](#)). SAEs, including deaths, will be listed for each event ([Listing 9](#)).

Narratives will be presented for all deaths, non-fatal serious adverse events, and subjects withdrawn due to adverse events.

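### SAP 2.9.3 ends the treatment-emergent period on the dosing day, against Protocol 8.3 and SAP 5.3, so the SAE and other TEAE tables omit events that start later but by the child's follow-up call

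*SAP*

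**What the plan says.** Protocol section 2 gives the secondary endpoints as "Incidence of AEs, TEAEs, SAEs, withdrawals due to TEAEs". SAEs stand there as their own item, with no treatment-emergent limit.

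The definition of treatment-emergent differs by place:

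- SAP 2.9.3 (Adverse Events) classes events "as treatment-emergent AEs if they occur on or after the treatment start date and time and before the next day", and everything later "as post-treatment AEs if they occur after the treatment date".
- Protocol 8.3 says that events after the first dose and "throughout the remainder of the study period (Follow-up Phone Call) will be considered TEAEs".
- Protocol 9.4.8 sets no end: "Treatment emergent AEs, those that occur after the first dose of study medication, will be summarized by treatment group".
- SAP 5.3 says that TEAE incidences "will also be tabulated by onset time (on-dosing day vs. post-dosing day"), which presupposes that a TEAE can start after the dosing day.

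SAP section 7 lists three incidence tables with SAEs in the title: "Table 4.4.3 Incidence of Treatment-Emergent SAEs by Preferred Terminology", and its study-eye and fellow-eye counterparts, Tables 4.4.5 and 4.4.7. All three are limited to treatment-emergent SAEs. SAP 5.3 has the same limit: "Treatment-emergent AEs associated with early terminations and serious AEs will be summarized by preferred term".

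Protocol 6.4.4 places the follow-up call 24 to 96 hours after dosing.

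**The concern.** The SAP's only explicit definition is the one in 2.9.3. A programmer who follows it will class an SAE that starts the day after dosing as post-treatment and leave it out of every table titled for SAEs. A programmer who follows Protocol 8.3, or who takes the onset split in SAP 5.3 at face value, will include it. The content of tables for a named secondary endpoint should not depend on which section is read.

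The truncation is not confined to SAEs. TEAEs and withdrawals due to TEAEs are also secondary endpoints, and their tables use the same definition. At worst, an arm's SAE table shows zero while Listing 9 holds an SAE that started in that arm during planned follow-up.

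**Working it through.** **Classification.** The documents give no figure to reproduce, so the check is to place one event under each definition. Take an SAE with onset after the dosing day and no later than that child's own call.

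| Output | SAP 2.9.3 window | Protocol 8.3 window |
|---|---|---|
| 4.4.3 (all SAEs); 4.4.5 or 4.4.7 if ocular | absent | counted |
| 4.2.2; 4.2.3 if above its 5% threshold; 4.2.5 or 4.2.6 if ocular; 4.4.1 | absent | counted |
| 4.4.2, 4.4.4, 4.4.6, if it led to discontinuation | absent | counted |
| 4.3.1-4.3.3, post-dosing-day column | always empty | counted |
| 4.2.4 (post-treatment AEs) | counted, seriousness not in the title | not counted |
| Listing 9 and narrative | present | present |
| 4.1.1, 4.1.2 (overall AE summaries) | shells not shown | shells not shown |

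The always-empty column shows that SAP 5.3 and SAP 2.9.3 cannot both be meant.

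**Share of follow-up outside the SAP window.** The call is 24-96 h after dosing (Protocol 6.4.4). Clinic hours of 08:00-17:00 are an assumption. Time left on the dosing day is 24 - 17 = 7 h to 24 - 8 = 16 h.

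- Call at 24 h: 24 - 16 = 8 h to 24 - 7 = 17 h lie outside, that is 8/24 = 33% to 17/24 = 71%.
- Call at 96 h: 96 - 16 = 80 h to 96 - 7 = 89 h lie outside, that is 80/96 = 83% to 89/96 = 93%.

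**Effect of one omitted SAE on an arm's entry** (exact Clopper-Pearson 95% limits; about 30 evaluable or 35 randomized per arm, from 60 and 70 in total):

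- 1/30 = 3.3% (0.1-17.2%) becomes 0/30 (upper limit 1 - 0.025^(1/30) = 11.6%).
- 1/35 = 2.9% (0.1-14.9%) becomes 0/35 (upper limit 1 - 0.025^(1/35) = 10.0%).

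**Chance that it happens.** The documents give no SAE rate. Assume a risk p per child of an SAE starting in the gap, and use 1 - (1 - p)^N.

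- p = 0.01%: 0.6% for N = 60 and 0.7% for N = 70.
- p = 0.1%: 5.8% for N = 60 and 6.8% for N = 70.

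**Ordinary TEAEs.** Table 4.2.3 shows preferred terms reported by more than 5% of an arm. With 30 per arm, two children (2/30 = 6.7%) pass and one (1/30 = 3.3%) does not, so a single non-serious event starting after the dosing day can decide whether a term is shown.

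**The case against.** The best defence is that no SAE is lost. SAP 2.9.3 and 5.3 list every SAE and require a narrative for every death and non-fatal SAE, with no treatment-emergent limit. Protocol 9.4.1 has data listed by treatment, so with about 30 children per arm a count can be read from Listing 9. Table 4.2.4 also counts the event as a post-treatment AE, and Tables 4.1.1 and 4.1.2 have no treatment-emergent limit in their titles and may carry an SAE row. All of this stands, and it is why the effect is minor. What it leaves is a table for an incidence endpoint that can disagree with the listing behind it, and two definitions that cannot both be programmed.

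It is also fair to say that the SAE table titles are ordinary and would be right under the Protocol 8.3 window. The fault lies in the window, and the fix belongs there.

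Three stronger readings are tempting, and the documents do not support them:

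- *That late SAEs go unreported.* Listing 9, the narratives and Table 4.2.4 show otherwise.
- *That any SAE on Days 2-5 falls inside planned follow-up.* Follow-up ends at each child's own call. A child called on Day 2 with no ongoing event is then complete (Protocol 6.4.4), so an event on Days 3-5 is outside even the Protocol 8.3 window.
- *That the tables should cover four weeks.* The four-week sentence in Protocol 8.3.3 concerns the investigator's duty to report SAEs to the sponsor; it does not define an analysis period.

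**Conclusion.** The point holds as a minor inconsistency. SAP 2.9.3 contradicts Protocol 8.3 and SAP 5.3, and followed as written it removes SAEs that start after the dosing day and by the child's call from Tables 4.4.3, 4.4.5 and 4.4.7. It truncates the other TEAE tables and the discontinuation tables in the same way.

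The classification rests on the text alone. The 33-93% share of follow-up rests on assumed clinic hours, and the 0.6-6.8% chance of an omitted SAE on an assumed risk; both are illustrations. For a single topical dose in healthy children, an SAE in the gap is unlikely. It cannot be settled whether the SAE endpoint is also tabulated without the limit, because the shells of Tables 4.1.1 and 4.1.2 are not shown.

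**What to change.** In SAP 2.9.3, define a TEAE as an AE with onset from the first drop through that subject's Follow-up Phone Call, in line with Protocol 8.3, and reserve the post-treatment class for onset after the call.

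The SAE, TEAE and discontinuation tables then count these events by arm under their present titles, and the dosing-day split in Tables 4.3.1-4.3.3 gains content. Rewording only the SAE tables would be worse: an SAE could then appear in Table 4.4.3 and be absent from the TEAE table 4.2.2. No extra row for events after the call is needed, since later spontaneous SAEs remain in Listing 9.

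The cost is a small SAP edit and minor reprogramming before lock. The protocol and the follow-up schedule stay as they are. The one visible side effect is that Table 4.2.4 will be nearly empty.
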